1. BACKGROUND

Gestational diabetes (GDM) is a condition in which carbohydrate intolerance develops during pregnancy. It remains one of pregnancy's most common medical complications, afflicting approximately 10% of all pregnancies in the United States (1). GDM is associated with maternal and fetal complications such as hypertensive disorders of pregnancy, birth injury, fetal macrosomia, cesarean section, neonatal complications, and increased risk of developing diabetes later in life (2). In addition, the Hyperglycemia and Adverse Pregnancy Outcomes (HAPO) study found that maternal hyperglycemia is associated with adverse perinatal outcomes of increased birth weight and neonatal hyperinsulinemia (3, 4). Timely diagnosis and treatment of GDM improves both maternal and fetal outcomes (5, 6).

To avert the multitude of the complications associated with GDM, universal screening is recommended at 24-28 weeks gestation (5, 7). Currently, screening and diagnosis of GDM can be made through various glucose challenge tests (8). Table 1 lists the current recommendations by various policy for GDM screening (7, 9, 10).

Table 1: GDM Screening Recommendations

Organization (Year)	Test	Criteria for GDM
		diagnosis
American Diabetes	Universal screening	FPG ≥ 92 mg/dL
Association (2020)	One Step	1h PG≥ 180 mg/dL
	2h PG (75 g OGTT)	2h PG ≥ 153 mg/dL
	Or	Or
	Two Step	1h ≥ 135 or 140mg/dL
	1h GCT (50g OGCT)/3h	Fasting ≥ 95 or 105 mg/dL
	OGTT (100g)	1hr ≥ 180 or 190 mg/dL
		2hr ≥ 155 or 165 mg/dL
		3hr ≥ 140 or 145 mg/dL

American College of Obstetrics & Gynecology (2018)	Universal screening Two-Step 1h PG (50 g OGCT) 3hr (100g OGTT)	
National Institute for Health & Care Excellence (2015)	Targeted high-risk screening One step 2h PG (75 g OGTT)	FPG ≥ 100mg/dL 2hr PG ≥ 140 mg/dL
WHO & FIGO (2013)	Universal screening One step 2h PG (75g OGTT)	FPG ≥126 mg/dL 2 h PG≥200 mg/dL
International Association of the Diabetes and Pregnancy Study Group (2010	Universal screening One step 2h PG (75g OGTT)	FPG ≥ 92 mg/dL 1h PG≥ 180 mg/dL 2h PG ≥ 153 mg/dL

Most institutions follow the American College of Obstetrics & Gynecology (ACOG) recommendations of a two-step assessment during 24 to 28 weeks gestation (2). However, there are at least four limitations of the 50g oral glucose tolerance test (GCT) diagnostic values. First, the one-hour GCT was validated to determine the risk of developing Type II diabetes later in life; the diagnostic cutoff, however, is not centered on preventing adverse maternal or fetal outcomes. Second, a positive one-hour GCT result requires pregnant people to return to the clinic while fasting to complete a three-hour glucose challenge test (GCT). Third, the predictive value changes in different ethnicities due to the varying prevalence of GDM (11). Fourth, there is no available screening test for people who present late to care or those who cannot tolerate the GCT (such as people after bariatric surgery or with significant nausea and vomiting). For those patients the most common management would be to panel their blood sugars for at least 1 week.

Other traditional diagnostic laboratory values, such as hemoglobin A1c and fasting blood glucose, used in non-pregnant states, have not been reliable or validated during pregnancy. HemoglobinA1c has poor sensitivity and specificity in the diagnosis of GDM, allowing for a high false-negative rate (12). Fasting blood glucose (FBG) was widely studied to decrease the burden associated with GTT, as it is associated with less cost and causes minor discomfort. However, no standardized criteria have been shown to provide reproducible GDM diagnosis (11).

Despite the high prevalence of GDM and complications, very few randomized trials studying the optimal screening test have been conducted (13). A recent randomized trial comparing the single step to the two-step diagnosis showed no difference in perinatal outcomes (14). A Cochrane review in 2015 cited that six small randomized control trials have been completed that have assessed optimal GDM screening. Of the six, only two studies compared the differences between recommended diagnostic tests (7). The findings are listed below.

Table 2: Randomized trials on screening for GDM

Title	RCT	N	Findings
Hillier et	RCT: 75g GTT v.	23,792	No difference in the primary outcome of a diagnosis of
al/2020 (14)	50g GCT/ 100g		GDM, LGA, CD, HDP, or perinatal composite
	GTT		
Olarinoye et	RCT: 75g GTT v.	248	Higher prevalence of GDM in 75g GTT group, No
al./2004 (12)	100g GTT		difference in macrosomia or FBG
Shirazian et	WHO 75g GTT v.	670	No difference in diagnosis of GDM, CD, macrosomia,
al/2008 (15)	ADA 75g GTT		instrumental birth

In the U.S., trends of obesity, sedentary lifestyle, cardiovascular disease, and many other risk factors that place patients at high risk of developing GDM are continuing to soar (16). However, with the adverse outcomes associated with GDM for both mother and infant, there is an urgent need to develop a comprehensive and standardized form of screening and diagnosis.

Continuous Glucose Monitoring in pregnancy

Continuous glucose monitoring systems putatively measure interstitial glucose values throughout the day, providing measurements every five minutes wirelessly. Providers are given many glucose values, including the mean, fasting, and range of glucose levels. Unlike a point of care value such as FBG or GTT result, CGM allows for much greater surveillance and detection of hyperglycemic episodes (9). Target values can be programmed into the receiver or mobile app, allowing for calculating time in range.

Prospective studies evaluating the accuracy of CGM during GTT assessed the efficacy of CGM to detect hyperglycemic excursions (17). In addition, CGM has been studied in high-risk patient groups to identify hyperglycemic episodes. CGM has detected abnormal glucose profiles and provided caregivers specific glycemic trends in multiple populations at risk for abnormal glycemic trends, such as morbid obesity, critically ill, polycystic ovarian syndrome (9).

Current two-step testing has many limitations, such as requiring a second diagnostic test that requires specific timing and prolonged laboratory stay (4 hours) with further delaying treatment and diagnosis. Unfortunately, no current

#UTHealtl

IRB NUMBER: HSC-MS-22-0153 IRB APPROVAL DATE: 07/05/2023 data uses CGM as a screening tool for GDM. CGM is a promising, minimally invasive modality that will provide a more comprehensive evaluation of the glycemic profile of people. Thus, allowing a prompt diagnosis and treatment tailored to each person's glycemic discrepancies recorded by the CGM.

2. RATIONALE FOR A CLINICAL TRIAL

There are multiple reasons for a clinical trial comparing the traditional method of screening for GDM versus

[figure not shown]
- Need for a diagnostic test that is based on maternal and neonatal outcomes.
- No current consensus on the best screening test for GDM during pregnancy.
- Non-pregnant diagnostic laboratory values, such as Hemoglobin A1c and fasting plasma glucose, do not have reliable diagnostic cut-offs during mid-pregnancy.
- Need for a test that can efficiently diagnose GDM, which does not require additional, lengthy clinic visits.
- The use of CGM permits for a complete glycemic profile as compared to the point of care glucose challenge test, thus allowing for a more specified and thorough treatment of GDM
- Readily available CGM results allow for prompt, individualized treatment.
- There are no current large, ongoing trials studying CGM as a screening tool for GDM.

3. HYPOTHESIS AND OBJECTIVE

3.1 Hypothesis:

We hypothesize that compared to usual care with the two- step screening method, CGM will increase detection of GDM and reduce maternal and neonatal adverse outcomes and health system costs related to GDM. CGM will also be shown to be highly cost-effective in preventing mother-infant dyads from developing maternal or neonatal adverse outcomes. Cost effectiveness may be achieved be either reducing maternal or neonatal health system costs without increasing the rate or heath system costs of adverse maternal or neonatal outcomes. By highly cost effective, we mean that CGM will lie within the dominant quadrant – i.e. the lower right quadrant – of the cost-effectiveness plane (Figure 1).

Figure 1. Cost Effectiveness Plane

3.2 Primary Objectives

The objectives of this randomized controlled trial are:

- To evaluate whether CGM for diagnosis of GDM and improves maternal and neonatal outcomes related to GDM.
- To evaluate whether CGM for GDM diagnosis reduces the health system costs for mother-infant dyads compared to usual care

3.3 PICO Question

Population: Pregnant individuals screening for GDM

Intervention: CGM for GDM screening

Comparison: Usual care with two step GDM screening

Primary Outcome: Composite neonatal outcomes

4. STUDY DESIGN AND POPULATION

4.1 Study Design

This is a single site, multi-clinic randomized controlled trial for pregnant people undergoing gestational diabetes screening in pregnancy.

4.2 Inclusion Criteria

- Maternal age of 18 years or older
- 24-30 weeks gestation undergoing GDM screening

4.3 Exclusion Criteria

- Known diagnosis of Type I and II DM
- History of bariatric surgery
- Multiple gestation pregnancy
- Major fetal anomalies
- Unwilling to use CGM for GDM screening

- Incarcerated subjects
- History of allergic reaction to any of CGM metals or adhesives in contact with the skin
- People with incompatible cellular devices with G6PRO application

5. METHODS AND ASSESSMENT

5.1 Randomization and blinding

- A non-clinical research team member will create computer-generated random sequences to ensure untampered randomization. A permutated block randomization in a random fashion 1:1 ratio will be employed to prevent imbalance in groups.
- Randomization will be stratified by BMI ≥ 40 and clinic site at randomization
- Blinding: The research team collecting data will be blinded to group allocation.
 We will not be able to blind the treating physician or patient to the CGM due to the nature of the intervention.

5.2 Setting

Recruitment will occur in outpatient clinic settings:

- University of Texas, Houston (UTH) outpatient clinics:
 - UT physicians' continuity clinic in the Texas Medical Center
 - Women's Health Center, Bellaire
 - Women's Health Center, Memorial City
 - Women's Health Center, Sugarland

5.3 Recruitment

- Flyers and posters will be placed in clinic work rooms, patient rooms and clinic restrooms with recruitment and study procedure information.
- The diabetes care and education specialist (CDCES) or research staff and collaborators will approach eligible individuals during their clinic appointment.
- The research team will introduce continuous glucose monitoring and the G6/G7PRO CGM device per the manufacturer's use instructions.
- Details of the study, risks and benefits of CGM in pregnancy will be discussed in a private room, and the informed consent form will be reviewed. Once all questions are answered and the individual is amenable to participant in the study, she will be asked to sign a consent form. A copy of consents will be given to the individual. In addition, patients will be approached about the study in either English or Spanish by research personnel fluent in the language.

5.4 Intervention and procedures

- After informed consent is completed; participants will be randomized into either one-hour GCT or CGM screening.
 - Group I will be comprised of one-hour 50g glucose challenge participants for diagnosis of GDM.
 - Group 2 will be participants that have CGM placement for diagnosis.
- CGM will consist of using the Dexcom G6 Pro device (Figure 2). The device will be applied by a trained health care professional in the clinic.
- The system will be set up according to the manufacturer's use instructions.
- The device will be placed on the abdomen or the arm.

- The sensor will stay in place for a maximum of 7 days as recommended by the manufacturer.
- In the event, CGM sensor malfunctions and values of at least three days are not available on Dexcom portal, sensor will be replaced.
- Sensors will not be reused for other patients.
- CGM will be placed for all study participants.
- Group I participants, CGM will be blinded and diagnosis will be based on 1-hour glucose challenge test results as below.
 - 1-hour result ≤ 130 mg/dL, the participant will have passed the challenge test.
 - 1-hour result ≥ 130 mg/dL will complete a three-hour 100g glucose tolerance test. If two out of three values are elevated per Carpenter Coustan criteria (Table 3), the participant will be diagnosed with GDM and treated according to the standard of care.
- Group 1 participants' CGM data will not be observed until completion of study and will not be available to provider.
- Group 1 participants will return transmitter at follow up visit after completion of 7 days. If unable to bring to clinic visit, a prepaid postage will be provided to the participant to return the transmitter.

Figure 2: Dexcom G6 Pro device

- Group 2 will use CGM for screening for diabetes.
- The Dexcom G6/G7 Pro App will be downloaded on the patient's phone
- A patient profile will be created on the Dexcom Clarity portal
- The patient will receive an email to link their portal to the clinic's portal
- If the patient's phone is not compatible with G6 Pro mobile app, the data will be blinded for her and the provider until the return of the device. Pick-up or mailing of the device will be planned for seven days after placement.
- The patient will receive a message through Epic EMR to remove the CGM one week after placement
- Group 2 will have the device in place for a total of 7 days and reviewed by the Diabetes team after 7-10 days after CGM placement. The recommended range for glucose during pregnancy is defined as 63-140 mg/dL (18). The time above range has been defined as ≥ 140 mg/dL, greater than 10% of total CGM

placement time. Based on the results of our prospective observational study of blinded CGM placement at time of one-hour GCT of pregnant people \leq 30 weeks a CGM metric of time above range \geq 10% was associated with higher rates of adverse neonatal outcomes.

- The following criteria will currently be used to diagnose gestational diabetes in the CGM group:
 - Time above range (≥140 mg/dL) ≥ 10% of the time while using CGM or
 - Average glucose≥130 mg/dL or
 - Any glucose value ≥200 mg/dL
- Group I will receive routine prenatal care follow-up depending upon one-hour glucose results as written above.
- Group 2 will complete CGM and proceed with treatment if positive screening is found, as written above.
- Management of GDM for both groups would include:
 - Consultation and follow up with Certified Diabetes Care and Education
 Specialist (CDCES)
 - The patients will be instructed to self-monitoring of blood glucose (SMBG)
 levels four times a day through a glucometer: fasting, 1-2 hour
 postprandial as recommended by the ACOG guidelines.
 - Patients will be managed according to the ACOG recommendations of goals (2):
 - Fasting: ≤ 95 mg/dL
 - 1 hour postprandial: ≤ 140 mg/dL

- 2 hour postprandial: ≤ 120 mg/dL
- Initiation of medication if consistently elevated blood sugars following diet adjustment per provider discretion
- Participants will be asked to continue to follow up as the standard of care.
- No extra visits will be scheduled
- Both groups will be followed throughout pregnancy, delivery, and postpartum.
- A release of records form will be signed at randomization so that in case the participant delivers at another center; we can still obtain records from the delivery.
- The research team will collect participant data, including demographic characteristics, medical history, obstetric history, labor course, and maternal and neonatal outcomes, by reviewing the electronic medical records and surveying the people during prenatal visits and the 6- week postpartum clinical appointment.
- All participants will receive a \$20 gift card after completing the diabetes screening (i.e., 1hGCT/3h OGTT if screened positive/7 days with GCM).
- All participants will receive a \$20 gift card following delivery.

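### Section 5.4 gives a 1-hour GCT of exactly 130 mg/dL two opposite instructions, and its OGTT rule counts three values where Table 1 lists four

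*Combined protocol and SAP*

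**What the plan says.** Group 1 is diagnosed by the two-step method, and section 5.4 sets out the steps.

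- **First step, pass:** "1-hour result ≤ 130 mg/dL, the participant will have passed the challenge test".
- **First step, refer:** "1-hour result ≥ 130 mg/dL will complete a three-hour 100g glucose tolerance test".
- **Second step:** GDM is diagnosed and treated if "two out of three values are elevated" by the Carpenter Coustan criteria, for which the section points to Table 3.

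Later in section 5.4, Group 1 follow-up is described only as "depending upon one-hour glucose results as written above", which adds no further rule.

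The one other place with cut-offs for these tests is Table 1 in section 1. Its two-step entry gives "1h ≥ 135 or 140mg/dL" for the 50 g test. For the 100 g test it lists "Fasting ≥ 95 or 105 mg/dL", "1hr ≥ 180 or 190 mg/dL", "2hr ≥ 155 or 165 mg/dL" and a fourth line for 3 hours (140 or 145 mg/dL).

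**The concern.** These lines decide which controls have the OGTT and which are treated for GDM. Two things in them do not fit together. The pass and refer branches of the first step share a boundary value. The second step counts values out of three, while the protocol's own table shows four for the same test.

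Three things are at stake.

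- **Detection.** Section 3.1 hypothesises that CGM will find more GDM than usual care. A control rule that counts fewer values than Table 1 lists could widen that difference for a reason unrelated to CGM.
- **The comparator.** Section 3.3 defines it as usual two-step care, so how well the control arm represents that care depends on the rule actually applied.
- **Planned secondary analyses.** Section 7.3 lists analyses of the GCT threshold and of a single abnormal OGTT value. The second cannot be defined until the counted values are fixed.

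Recruitment runs through four clinics (section 5.2) and treating physicians are not blinded (section 5.1), so different staff could resolve the ambiguity differently.

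**Working it through.** **First step (GCT).** Let x be the 1-hour result in mg/dL. Section 5.4 passes x ≤ 130 and refers x ≥ 130. The two sets overlap at x = 130 and nowhere else, and together they cover every result. One value therefore has two opposite instructions. The later text in section 5.4 only refers back to these lines. Table 1 uses 135 or 140 for this test, so it does not settle what happens at 130.

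**Second step (OGTT).** Table 1 lists four values: fasting (F), 1 h, 2 h and 3 h. Section 5.4 counts three and does not itself name them. The plan gives no figure to reproduce, so the check compares the two counts. Each value is either elevated or not, which gives 2⁴ = 16 patterns.

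- At least two of four elevated: C(4,2) + C(4,3) + C(4,4) = 6 + 4 + 1 = 11 patterns.
- At least two of a fixed three elevated: C(3,2) + C(3,3) = 3 + 1 = 4 patterns of the counted values. The uncounted value may be either, so 4 × 2 = 8 patterns.
- Lost: 11 − 8 = 3. Two elevated among three counted values always means at least two among four, so newly positive patterns = 0.

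The three lost patterns are those where the uncounted value and exactly one other are elevated:

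| Value not counted | Patterns no longer positive |
|---|---|
| Fasting | F+1h, F+2h, F+3h |
| 1 h | F+1h, 1h+2h, 1h+3h |
| 2 h | F+2h, 1h+2h, 2h+3h |
| 3 h | F+3h, 1h+3h, 2h+3h |

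The 4 + 1 = 5 patterns with three or four elevated values stay positive whichever value is left out. Each of the 6 patterns with exactly two elevated values is lost under 2 of the 4 possible omissions.

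**Single abnormal value (section 7.3).** Exactly one of four elevated is C(4,1) = 4 patterns. Exactly one of a fixed three is C(3,1) × 2 = 6 patterns. The three patterns that lose the diagnosis move into this group, and the pattern in which only the uncounted value is elevated moves out: 4 + 3 − 1 = 6.

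These are counts of possible patterns. The documents give no distribution of GCT or OGTT results, so they cannot be turned into numbers of participants or events.

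**The case against.** The best case against the point is that it is small and partly rests on what cannot be seen.

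- **Table 3.** Section 5.4 cites it for the OGTT criteria, and it may list the values that count. Its absence from the available text is not a fault of the plan. This stands, and it is why the conclusion on the OGTT is conditional. Even so, the count in section 5.4 would still need to be reconciled with Table 1.
- **Table 1 is background.** It summarises organisations' recommendations, offers alternative cut-offs and does not name Carpenter Coustan. This also stands: only the 130 mg/dL overlap lies wholly inside section 5.4, and the OGTT mismatch is between that section and the Background.
- **Three may be a one-word slip.** It may be. Nothing shows that a value is ignored in practice, and the pattern counts apply only if one is.
- **The ≤ sign could have been misread when the text was extracted.** That is possible, but nothing shows it happened.
- **Little reaches the endpoint.** The primary outcome is a neonatal composite analysed by intention to treat (sections 6.1 and 7.2), and the GDM diagnosis rate is not listed as an outcome in section 6.2. This limits the consequence for the main result. It does not make the written rule usable at 130, and detection remains part of the stated hypothesis.
- **Section 7.1 speaks of 734 individuals diagnosed with GDM, so diagnosis counts might bear on sample size.** However that sentence is read, the 367 per group and Table 4 do not change.

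**Conclusion.** The concern holds. As written, the control-arm rule cannot be followed consistently at a GCT of exactly 130 mg/dL, and its OGTT count does not match the only table of values in the available text. The first conflict affects referral at that single value. The second matters only if a three-value rule is really used. At the same cut-offs, it would keep 8 of 11 positive patterns, whichever value is left out, and add none, so control-arm diagnoses could only stay the same or fall.

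Confidence is high that the wording conflicts. It does not extend to whether a three-value rule is applied in practice. The sample size calculation and Table 4 are unaffected, and the effect on the primary composite is probably small. The point should be corrected because these are operative rules for classifying and treating one arm, but it does not threaten the trial's main comparison.

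**What to change.** The investigators should:

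1. Reconcile the two GCT lines in section 5.4 so that every result falls in exactly one branch.
2. Reconcile the OGTT count in section 5.4 with Table 3 and Table 1, and state the intended rule once, naming the values that count.
3. If any controls have already been tested, confirm that those with a GCT of exactly 130 mg/dL or with an OGTT were classified by that rule.

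The choice of cut-off and count is theirs. The cost is one or two sentences in section 5.4 and, if testing has begun, a record check limited to those controls.

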6. OUTCOME MEASURES

6.1 Primary outcome:

 Composite Adverse Neonatal Outcome including one or more of the followings: (time frame: from enrollment to discharge)

- Large for gestational age (LGA): weight over 90th percentile of the expected value according to gestational age (using the nomogram by Duryea EL et al). (19)
- Shoulder dystocia: defined as the need for any extra maneuvers, other than gentle downward traction of the fetal head to deliver the fetal body after the fetal head has been delivered
- Birth injury: skull, clavicular, humerus fracture, or brachial plexus injury
- Neonatal hypoglycemia defined as requiring intravenous or oral glucose
- Respiratory distress: the need for at least 4 hours of respiratory support with supplemental oxygen, continuous positive airway pressure, or ventilation at the first 24 hours of life
- Fetal or neonatal death (within 28 days of birth)

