- Neonatal hypoglycemia defined as requiring intravenous or oral glucose
- Respiratory distress: the need for at least 4 hours of respiratory support with supplemental oxygen, continuous positive airway pressure, or ventilation at the first 24 hours of life

#UTHealth

- Fetal or neonatal death (within 28 days of birth)
- Apgar score < 7 at 5 min
- Neonatal intensive care unit (NICU) admission
- NICU length of stay
- Neonatal hypoglycemia: ≤40 mg/dL in the first 24 hours of life and less than 50 mg/dL after or requiring medical therapy
- Neonatal polycythemia defined as hematocrit (Hct) or hemoglobin (Hgb)
 level above the upper limit of normal (>2 standard deviations) for
 gestational and postnatal age.
- Neonatal hyperbilirubinemia requiring phototherapy
- Maximum bilirubin level
- Umbilical cord pH (arterial and venous)
- Need for intravenous glucose therapy
- Small for gestational age, defined as a weight below 10th percentile of the expected value according to gestational age (using the nomogram published by Duryea EL et al) (19)

Mother-Infant Dyad

- Total health system costs for mothers and infants
- Cost-effectiveness of CGM relative to usual care, assessed as the total
 incremental maternal and neonatal health system costs (savings) per
 prevented mother-infant dyad from developing a maternal adverse outcome
 (preterm birth, induction of labor, pregnancy-induced hypertension, admission
 for poor glucose control, primary cesarean section, postpartum hemorrhage,

#UTHealth

IRB NUMBER: HSC-MS-22-0153

endometritis or wound complications) or a neonatal adverse outcome (LGA, shoulder dystocia, birth injury, neonatal hypoglycemia, respiratory distress, fetal or neonatal death within 28 days of birth).

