7. SAMPLE SIZE AND STATISTICAL METHODS

7.1 Determination of Sample Size

As stated above, based on the results of our prospective observational study of blinded CGM placement at time of one-hour GCT of pregnant people ≤ 30 weeks

#UTHealth

IRB NUMBER: HSC-MS-22-0153 IRB APPROVAL DATE: 07/05/2023 gestation we would like to adjust the sample size for this trial. A CGM metric of time above range ≥ 10% was associated with higher rates of adverse neonatal outcomes of preterm birth, intravenous glucose therapy and longer hospitalization. The findings of this study serves as the basis of diagnosis of GDM through CGM for our trial. Based on the results of this prospective trial the estimated rate of the primary outcome was 40%. In this trial we would include a more diverse population with a lower rate of factors associated with GDM such as lower BMI, different race and ethnicity. Our assumption is that the rate of the primary outcome will be 25%.

Sample size calculations using a Bayesian analysis with different probability thresholds are presented in Table 4. In order to detect a 30% reduction in the rate of adverse neonatal outcome between the control and intervention with 90% power and a Bayesian posterior probability of 75% (of any reduction), 734 individuals (367 per group) will need to be diagnosed with GDM. With a 10% loss to follow up, 816 people in total will need to be enrolled. A total of 1020 individuals would need to be approached, to accommodate an expected enrollment rate of 80%.

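### Section 7.1 requires 734 participants diagnosed with GDM, but its own arithmetic makes them all followed participants; separately, a supportive composite without treatment-defined hypoglycemia would be a cheap addition

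*Combined protocol and SAP*

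**What the plan says.** **Population.** Section 7.1 assumes a 25% control rate and a 30% reduction, sets a 75% posterior-probability threshold, and concludes that "734 individuals (367 per group) will need to be diagnosed with GDM". It then allows 10% loss to follow-up to reach 816 enrolled, and an 80% enrollment rate to reach 1020 approached. Section 4.2 admits adults at 24-30 weeks who are undergoing screening. Section 5.4 randomizes them after consent to one of the two screening methods, so diagnosis comes after randomization. Section 7.2 specifies intention to treat.

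**Outcome.** In section 6.1 any one component makes an infant a case. One component is "Neonatal hypoglycemia defined as requiring intravenous or oral glucose"; no glucose value is needed. Section 3.1 expects that "CGM will increase detection of GDM". Section 5.1 states: "We will not be able to blind the treating physician or patient to the CGM due to the nature of the intervention". It also says that the staff who collect data are blinded to allocation. Section 5.4 has them obtain "maternal and neonatal outcomes, by reviewing the electronic medical records".

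Section 6.2 lists every component again as a separate secondary outcome. It adds a second hypoglycemia outcome with glucose thresholds, which also counts infants given medical therapy, and "Need for intravenous glucose therapy". The neonatal part of the cost-effectiveness outcome also includes hypoglycemia. Section 7.2 plans a logistic model and a Bayesian binomial model for the primary composite, with no supportive version of it. Section 7.3 plans an analysis of risk factors for neonatal hypoglycemia and several analyses of composites that it does not define; none is this comparison by arm. Section 10.1 refers to an attached list of variables, which is not in the text available for this review.

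**The concern.** The 734 sentence names a different population from the one that the rest of the plan enrolls and analyzes. Read literally, it would restrict the primary analysis to diagnosed participants. That is a subgroup formed after randomization, by a different test in each arm. It also leaves unclear whose event rate the 25% is.

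The second issue arises only if all randomized participants are analyzed. The share of mothers with a GDM label is expected to differ by arm, and clinicians know the label. If newborns of labeled mothers are tested and given glucose more often, some infants in the CGM arm become cases because of the label. A weak or null primary result could then not be traced to, or cleared of, this mechanism. Separate component rates do not show exactly how many infants are cases through glucose treatment alone.

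**Working it through.** **A. The 734**

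1. 2 x 367 = 734. 734/(1 - 0.10) = 815.6, rounded up to 816. 816/0.80 = 1020. The plan's figures reproduce.
2. In reverse, 816 x 0.90 = 734.4 followed. For 734 to be diagnosed, every followed participant would have to be diagnosed, although diagnosis is not an entry criterion.
3. Section 1 puts GDM at about 10% of US pregnancies, a background figure and not a trial estimate. 816 x 0.10 = 81.6, about 82 diagnoses.
4. Power at 367 analyzed per group, 0.25 against 0.175, was computed with a normal approximation on log RR, the section 7.2 prior (mean 0, SD = ln(3.3)/1.96 = 0.609) and exact enumeration of two binomials. It is 0.965 at the 75% threshold and 0.786 at 95%; Table 4 has 0.97 and 0.80. So 367 is the number analyzed per group. (Section 7.1 quotes 90% power at 75%, where Table 4 has 0.97; that is a separate matter.)

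**B. Possible size of a label-driven shift**

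The documents give no component rates, no expected difference in diagnosis and no link from label to newborn treatment. All inputs here are assumed: 5-10 extra points of diagnosis in the CGM arm, 10-20 points of excess glucose treatment, and 70% of those infants not otherwise cases. Offset = product of the three, added to the CGM arm. Apparent RR = (0.175 + offset)/0.25, or (0.25 + offset)/0.25 with no effect.

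| Inputs | Offset (points) | RR if true 0.70 | Power at 75% | RR if no effect | Chance of passing 75%, no effect |
|---|---|---|---|---|---|
| none | 0 | 0.700 | 0.965 | 1.000 | 0.242 |
| 0.05 x 0.10 x 0.70 | 0.35 | 0.714 | 0.955 | 1.014 | 0.209 |
| 0.05 x 0.20 x 0.70, or 0.10 x 0.10 x 0.70 | 0.70 | 0.728 | 0.942 | 1.028 | 0.179 |
| 0.10 x 0.20 x 0.70 | 1.4 | 0.756 | 0.908 | 1.056 | 0.128 |

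Power falls to 0.90 at an offset of 1.53 points.

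A wider assumed set has labels in 10% of controls and 15-30% of the CGM arm, with 10-30% extra treatment among labeled mothers' infants who are not already cases, in both arms. It gives an apparent RR from (0.175 + 0.825 x 0.15 x 0.10)/(0.25 + 0.75 x 0.10 x 0.10) = 0.73 to (0.175 + 0.825 x 0.30 x 0.30)/(0.25 + 0.75 x 0.10 x 0.30) = 0.91 (0.915 unrounded). Power at 75% runs from 0.95 down to 0.50.

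**C. What the planned outcomes already show**

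In each arm, (composite cases - hypoglycemia cases) ≤ cases without hypoglycemia ≤ composite cases. The largest other component is also a lower bound, and the sum of the others an upper bound. The restricted count can therefore be bounded, but not obtained exactly, because one infant can have several components.

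**D. A composite without hypoglycemia, 367 per group**

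Assume hypoglycemia-only cases are a share s of the composite. The rates are then 0.25(1 - s) and 0.175(1 - s). The no-effect columns come from 400,000 simulated trials without bias.

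| s | Rates | Power at 75% | Either composite passes 75%, no effect | Opposite sides of 75%, no effect |
|---|---|---|---|---|
| 10% | 0.225, 0.1575 | 0.949 | 0.291 | 0.049 + 0.043 = 0.092 |
| 20% | 0.200, 0.140 | 0.929 | 0.308 | 0.066 + 0.064 = 0.130 |
| 30% | 0.175, 0.1225 | 0.906 | 0.319 | 0.078 + 0.080 = 0.158 |
| 40% | 0.150, 0.105 | 0.868 | 0.338 | 0.095 + 0.091 = 0.186 |

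The primary composite alone passes 75% in 0.242 of trials with no effect. With a true RR of 0.70 on every component, the two composites fall on opposite sides in 0.023 + 0.006 = 0.029 of trials at s = 10% and 0.105 + 0.009 = 0.114 at s = 40%.

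**The case against.** On the 734, a reader might infer that the trial is about ten times too small: at 10% prevalence, 734 diagnosed and followed would need 734/0.10 = 7,340 followed and 7,340/0.90 = 8,156 enrolled. The documents do not support this. Entry criteria, timing of randomization, loss allowance, approach figure and intention to treat all point to 734 followed participants of any diagnosis. The sentence is wrong; the enrollment arithmetic is not.

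On hypoglycemia, the case against is strong:

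- **The causal step is not documented.** Section 5.1 names only the treating physician and the patient as unblinded, and nothing says that newborn staff act on the label. The unseen variable list may cover newborn glucose items. This stands and keeps the severity low.
- **Mitigations exist.** The threshold-based secondary helps, though it also counts therapy and otherwise depends on a test having been done. Blinded data collection limits bias in abstraction, but not in a treatment decision already taken. The bounds in part C are a real answer, though not an exact one.
- **Dropping one component does not isolate the mechanism.** Respiratory distress is defined by support given and shoulder dystocia by maneuvers used. This stands: the restricted composite is not free of clinicians' decisions.
- **Care prompted by the label is part of the strategy's effect.** This stands and is a reason to keep the component.

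A reader might also infer that the primary composite is invalid or could produce a false benefit for CGM. Neither follows. With more labels under CGM, as section 3.1 expects, the shift runs against CGM and lowers the chance of passing under no effect. It would reverse only if CGM labeled fewer mothers.

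**Conclusion.** Two conclusions hold, with different weight.

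The requirement that 734 be diagnosed is wrong as written, on the plan's own figures. This needs no outside assumption: 816 enrolled with 10% loss leaves 734 followed in total. The figure of about 82 diagnoses rests on the background prevalence and only illustrates the gap. The wording matters because it decides the analysis set. If only diagnosed mothers were analyzed, all would carry the label and the hypoglycemia question would largely disappear.

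The missing composite without hypoglycemia is a low-severity gap. The size of any shift is unknown: the assumed inputs turn a true RR of 0.70 into 0.71-0.76 on the narrower set and about 0.73-0.92 on the wider one, and neither set has a source in the documents. What can be said is that the component is defined by treatment, the label is expected to differ by arm, and planned reporting allows bounds but not the exact per-infant result. This is a cheap improvement, not a design error.

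**What to change.** **Section 7.1.** Reword so that 734 (367 per group) are randomized participants with primary-outcome data, whether or not diagnosed with GDM, and state that the 25% control rate applies to that population. This costs one sentence.

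**Section 7.2.** Keep the primary composite unchanged and add, for example:

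> A supportive analysis will repeat the primary logistic and Bayesian models for the composite without the neonatal hypoglycemia component, in the same analysis set and with the same handling of missing outcomes. Infants whose only event was glucose treatment will be tabulated by arm. Both will be reported whatever the primary result. This analysis does not replace the primary result and cannot support a claim of efficacy. A difference between the composites may reflect ascertainment, a true effect on hypoglycemia, or chance.

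Tying it to the primary analysis set, and not to all randomized participants, respects the expected 10% loss.

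**Cost.** One analysis and one table, from data already needed for the primary outcome. The downsides, if 10-40% of cases are hypoglycemia-only (assumed), are fewer events (power about 0.95-0.87 at the 75% threshold), a second look (0.24 rising to 0.29-0.34 under no effect), and disagreement by chance in 9-19% of trials with no effect. The 75% figure is the sample-size threshold of section 7.1; section 7.2 promises to report probabilities but states no decision rule, so the bar on efficacy claims should be explicit.
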